At the end of the study, the MTD will be inferred based on the DLT data and all safety data observed at all dose levels. The specific MTD estimation method is shown in Section 4.2. The RPTD will be established by taking into consideration of the PK and/or PD profiles and safety data from the dose escalation phase.

The DLT evaluable subject is defined as the subject who received at least 75% of the planned doses of treatment and completed the safety assessment during DLT evaluation period.

During the DLT evaluation period, Subject can withhold 3D185 due to drug-related AEs. If the withholding time is more than 7 days, the AE will be considered as DLT. The subject's dose of 3D185 will not be reduced unless DLT occurs.

4.2. i3+3 Design

Similar to the 3+3 design^[18], the i3+3 is rule-based design, and it is also an interval-based design similar to mTPI^[19]. The specific algorithm of i3+3 design is shown in Appendix 7. Compared to the 3+3 design, the i3+3 design offers greater flexibility (e.g., flexible handling of subject, shedding), higher MTD selection probabilities, and better safety (see Appendix 8 for the comparison results of the simulation trials for 3+3 and i3+3). The target toxicity probability of the MTD in this study is set to pT = 25%, and the equivalence interval (EI) is (16%, 30%). This means

that the MTD should have a toxicity probability near 25% but not below 16% or above 30%. The decision table for the i3+3 design of this study is shown in Figure 1.

[figure not shown]

Figure 1 i3+3 Dose Escalation Decision Table

Note:

This is a decision table for the 3D185 dose-finding study. The target toxicity probability (pT) is 25% and the equivalence interval (EI) is (16%, 30%) for 42 subjects. Each column represents (n) number of DLT evaluable subjects treated at the current dose and each row represents (x) number of subjects with DLTs at the dose level. Each cell in the table provides the dose-assignment recommendation based on the readouts from the corresponding row (x) and column (n). The letters in the decision table represent different dose-assignment recommendations.

The i3+3 dose-escalation phase is expected to enroll 30-42 subjects (maximum sample size will be adjusted according to the first dose entering the i3+3 phase. For details, see Section 4.1). Every 3 subjects as a cohort will be sequentially enrolled.

The specific operation process of i3+3 design is as follows:

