- ♦ Three subjects will be enrolled in a cohort to receive the planned dose of 3D185. When i3+3 dose-escalation phase starts, if there is no Grade ≥ 2 drug-related AE occurs during the accelerated titration phase, the subjects in the first cohort in this phase will receive 100 mg 3D185. Otherwise, one of the subjects from the accelerated titration dose-escalation cohort will be enrolled in the first cohort of the i3+3 phase. And 2 additional subjects will be enrolled in this first cohort.
- After the three subjects in each cohort complete the DLT evaluation, the dose-assignment recommendation for the next cohort will be determined according to the decision table (Figure 1) by using the safety data from the DLT evaluable subjects.
 - 1) In Figure 1, "E" stands for escalating to the next higher dose; "S" stands for staying at the current dose; "D" stands for de-escalating to the previous lower dose.
 - 2) "DU" indicates that the toxicity at the current dose level is too high. Thence, it stands for de-escalating to the previous lower dose and marking the current and the higher doses as unacceptable so that it will never be used again in the remainder of the trial to avoid other subjects receiving treatment at these doses to ensure their safety. If the current dose is the lowest dose and the dose-assignment recommendation is "DU", the study should be terminated to ensure the safety and no dose level will be selected as the MTD.
 - 3) If the current dose is the lowest dose and the dose-assignment recommendation is "D", the study will continue to enroll new subjects at the current dose. Once the dose-assignment recommendation is "DU", the study should be terminated to ensure safety.
 - 4) If the current dose is the highest dose and the dose-assignment recommendation is "E", the study will continue to enroll new subjects at the current dose.
 - 5) Figure 1 is still applicable in the situation of subjects who have withdrawn due to some reason or more than 3 subjects enrolled in the current dose cohort. For example, if one of three enrolled subjects have withdrawn from the study due to some reasons, the i3+3 design will always appropriate to make a decision based on the data from the remaining 2 DLT evaluable subjects.

 \diamond Repeat the steps of 1) and 2) until the maximum sample size is reached.

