After all of the subjects have enrolled and the observations have completed, isotonic regression will be used to select the MTD based on the observed DLT data and all safety data from all the dose levels^[19]. That is, if the toxicity probability of a dose is close to the target toxicity probability

after isotonic estimation, the dose will be selected as the MTD. In the case where the estimates of the toxicity probability of the two doses are consistent, if the estimate is less than the target toxicity probability, the higher dose will be selected as the MTD; if the estimate is greater than or equal to the target toxicity probability, the lower dose will be selected as the MTD. The MTD selection process can be implemented in the U-Design (https://udesign.laiyaconsulting.com/decision).

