APPENDIX 8 SIMULATION TEST FOR i3+3 AND 3+3 DESIGNS

Simulation setup

[figure not shown]
We conducted a simulation trial using U-Design v1.1.5 (udesign.laiyaconsulting.com). The statistical performance of the i3+3 and 3+3 (Storer, 1989) designs was compared according to the study setup of the 3D185 phase 1 clinical trial in China. In this study, there are 7 escalating dose levels will be evaluated, the first two dose levels will use accelerated titration dose-escalation design, and the remaining five dose levels will use i3+3 dose escalation design. If a Grade ≥ 2 drug-related AE occurs during the accelerated titration phase, the current dose level will become the initial dose level in the i3+3 phase. Therefore, the initial dose of the i3+3 may have three different conditions: 100 mg (Cohort 3), 50 mg (Cohort 2), or 25 mg (Cohort 1). And the maximum sample size in each condition will be 30, 36, and 42, respectively. Each cohort will enroll 3 subjects. The MTD target toxicity probability pT = 25%, the choice of $\varepsilon 1$ is 0.09, and the choice of $\varepsilon 2$ is 0.05, so the EI is (16%, 30%). We simulated six different scenarios (Table 12) and three different starting dose settings, and performed 1,000 simulations for each of the "Scenario* Starting Dose".

Scenarios	рТ (%)	Times	True Toxicity Probability of Each Dose						
Scenarios	p1 (70)	Times	Dose 1	Dose 2	Dose 3	Dose 4	Dose 5	Dose 6	Dose 7
1	0.25	1000	0.1	0.25	0.35	0.45	0.55	0.65	0.75
2	0.25	1000	0.04	0.08	0.13	0.2	0.25	0.35	0.5
3	0.25	1000	0.04	0.08	0.12	0.16	0.2	0.24	0.28
4	0.25	1000	0.38	0.43	0.48	0.53	0.58	0.63	0.68
5	0.25	1000	0.04	0.08	0.12	0.16	0.45	0.55	0.65
6	0.25	1000	0.05	0.1	0.42	0.49	0.57	0.64	0.7

Simulation results (i3+3 vs 3+3)

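### The MTD selection step in Section 4.2 states no eligible set of doses, so it can name a dose marked unacceptable and does not yield the Appendix 8 results

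*Protocol*

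**What the plan says.** Four statements in the protocol bear on which dose may become the MTD.

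- **Meaning of the interval (4.2, opening paragraph).** With a 25% target and a 16-30% equivalence interval, the section explains "that the MTD should have a toxicity probability near 25% but not below 16% or above 30" per cent.
- **DU rule (4.2, operating steps).** A DU decision de-escalates and has the effect of "marking the current and the higher doses as unacceptable so that it will never be used again in the remainder of the trial". Only one DU clause mentions the MTD. It covers DU at the lowest dose, where "the study should be terminated to ensure the safety and no dose level will be selected as the MTD".
- **Final selection (4.2, last paragraph).** After the last observation, "isotonic regression will be used to select the MTD based on the observed DLT data and all safety data from all the dose levels". A dose is chosen "if the toxicity probability of a dose is close to the target toxicity probability" after isotonic estimation. Equal estimates are resolved by a tie rule: below target the higher dose is taken, and otherwise "if the estimate is greater than or equal to the target toxicity probability, the lower dose will be selected as the MTD". No condition on eligibility appears in this paragraph.
- **Simulated performance (Appendix 8).** For i3+3 starts at 100, 50 and 25 mg, "the maximum sample size in each condition will be 30, 36, and 42, respectively". Tables 13, 14 and 15 give Scenario 6 correct-selection probabilities of 0.849, 0.885 and 0.883.

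Section 4.1 points to 4.2 as the place where the MTD estimation method is specified.

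**The concern.** Finding the MTD is a primary objective, and the MTD feeds the recommended dose. The paragraph that performs the selection uses only distance from 25%. A dose can be marked unacceptable during the trial and still lie nearer to 25% than the dose below it, if the dose below has shown almost no toxicity. The DU rule and the selection rule then point to different doses on the same data, and the text does not say which prevails.

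There is a second consequence. The simulations in Appendix 8 are the protocol's evidence that the design performs well. If they were produced with a stricter selection rule than the one written in 4.2, they do not describe the written rule.

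**Working it through.** **Inputs.** From 4.2 and Appendices 7 and 8: target 0.25, interval 0.16-0.30, cohorts of 3, maximum 30/36/42 subjects, the E/S/D algorithm, the tie rule and the true toxicity rates in Table 12. **Assumed**, because Figure 1 is not shown and the text gives no formula: DU applies when Pr(p > 0.25) exceeds a cut-off c, with p following Beta(1+x, 1+n-x). The values c = 0.90, 0.95 and 0.99 were run.

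**Step 1: where DU begins.** The posterior tail equals a binomial tail: Pr(p > 0.25) = Pr(Bin(n+1, 0.25) ≤ x). At c = 0.95, DU begins at 3/3, 4/6, 5/9, 6/12, 7/15 and 8/18. For 7/15, Pr(Bin(16, 0.25) ≤ 7) = 0.973.

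**Step 2: when a DU dose wins.** If the dose below has an estimate of 0, its distance from target is 0.25. A DU dose with observed rate r is nearer only if r - 0.25 < 0.25, that is r < 0.50. On the c = 0.95 boundary the first such point is 7/15 = 0.467, so about 15 subjects are needed at that dose. This is why the event is uncommon.

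**Step 3: a path the rules permit (100 mg start, 30 subjects).** 150 mg alternates with 100 mg, which stays free of DLTs.

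| 150 mg | x/n | (x-1)/n | Decision |
|---|---|---|---|
| 1/3 | 0.333 | 0 | S |
| 2/6 | 0.333 | 0.167 | D |
| 3/9 | 0.333 | 0.222 | D |
| 4/12 | 0.333 | 0.250 | D |
| 7/15 | 0.467 | - | DU |

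100 mg ends at 0/15, so the total is 15 + 15 = 30. The distances from target are |0.467 - 0.25| = 0.217 for 150 mg and |0 - 0.25| = 0.25 for 100 mg. The written rule selects 150 mg, the dose just closed. With DU doses ineligible, the same rule selects 100 mg.

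**Step 4: how often.** Simulating the design and selecting from all treated doses:

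| DU cut-off | DU dose named, Scenario 6 |
|---|---|
| 0.90 | about 11-12% |
| 0.95 | about 3-4% |
| 0.99 | about 0.5% or less |

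At 0.95 the other scenarios give about 1% or less (highest run 1.3%). In no simulated case did the selected DU dose have an isotonic estimate at or below 30%.

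**Step 5: reproducing Appendix 8 (c = 0.95).**

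| Setting | Stated | Rule as written | DU doses excluded | Estimates above 30% excluded |
|---|---|---|---|---|
| Scenario 6, 100 mg start, correct | 0.849 | 0.61-0.62 | about 0.645 | 0.846-0.855 |
| Scenario 6, 50 mg start, correct | 0.885 | 0.62-0.63 | 3-4 points higher | 0.880-0.884 |
| Scenario 6, 25 mg start, correct | 0.883 | 0.62-0.63 | 3-4 points higher | 0.884-0.888 |
| Scenario 4, 25 mg start, no selection | 0.844 | about 0.68 | about 0.68 | about 0.85 |
| Scenario 1, 50 mg start, correct | 0.516 | 0.636 | 0.629 | 0.518 |

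With 1,000 simulated trials, the standard error of 0.849 is √(0.849 × 0.151 / 1000) = 0.011. The gap of 0.849 - 0.62 = 0.229 is about 20 standard errors. The mismatch does not come from the assumed cut-off: for Scenario 6 from 100 mg the written rule gives 0.701, 0.607 and 0.545 at 0.90, 0.95 and 0.99. Only the 30% cap reproduces the tables.

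**The case against.** The strongest reply is that 4.2 already says the MTD should not exceed 30%, which would rule out the 46.7% dose in the example. That is correct as far as it goes. If the selection step applied this limit, it would have blocked every simulated case. But the limit appears as an explanation of the interval and is not carried into the selection paragraph. Nor can the sentence be the operating rule as it stands, because it is two-sided. Applied to the isotonic estimates in Scenario 6 from 100 mg, it leaves no eligible dose in roughly three quarters or more of trials, whereas Table 13 states 0.014 for no selection. Appendix 8 also treats Dose 2, with true toxicity 10%, as the Scenario 6 MTD, which is below the 16% floor.

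Three further points have weight.

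- The words about all dose levels name the data used in the fit, which is proper for isotonic regression. They do not say that every dose is a candidate. The defect is the silence on candidates.
- The DU clause is framed around further treatment, and its one mention of the MTD excludes it. That supports reading unacceptable as ineligible, but it settles only the lowest-dose case.
- U-Design may apply a limit internally. The protocol says only that the selection can be implemented there, so this cannot be confirmed.

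Leaving the candidate set to a statistical analysis plan would be ordinary practice, but here the protocol states the rule itself and refers to 4.2 for it.

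**Conclusion.** The point holds as a gap between passages that must be reconciled. The selection paragraph omits both limits that the rest of 4.2 implies. Read literally, it can name a closed dose, and it does not produce the operating characteristics in Appendix 8.

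The first consequence is modest and depends on the assumed DU cut-off: about 3-4% of trials at 0.95 in the least favourable scenario, with a range from about 0.5% or less to about 12%. The second is larger and does not depend on that assumption: 0.55 to 0.70 against a stated 0.849.

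Three stronger readings are tempting and unsupported. A reader might infer that the protocol expressly makes DU doses candidates; it is silent. A reader might infer that closed doses would often be chosen in practice; outside Scenario 6 the rate at 0.95 is about 1% or less, and the software's own rule cannot be seen. A reader might infer that excluding DU doses alone would restore the Appendix 8 performance; it recovers only about 3-4 points in Scenario 6 at 0.95, and it adds nothing once the 30% cap is applied. Nor do these results show the Appendix 8 simulations to be wrong: they fit a one-sided cap that 4.2 does not state as a selection rule.

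**What to change.** State the candidate set in the last paragraph of 4.2 and align it with the interval statement, the DU rule and Appendix 8. Suggested content: doses marked DU, all doses above them, and doses whose isotonic estimate exceeds the upper limit used in the Appendix 8 simulations are not candidates for the MTD; their data remain in the isotonic fit. State whether the 16% lower bound plays any part in selection. Confirm that U-Design is run with the same rule, and repeat this in the statistical analysis plan. If the sponsor intends the uncapped rule instead, Appendix 8 needs to be re-run under it.

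The cost is a few sentences. The statistical price lies in Scenario 1, where the closed or capped dose may truly be near target. DU exclusion alone lowers correct selection there by up to about 1 point at a 0.95 cut-off (0.636 to 0.629 from the 50 mg start). The 30% cap lowers it by roughly 9-12 points against the literal rule (0.636 - 0.518 = 0.118 from the 50 mg start). That brings it to about the level Appendix 8 already reports, so no stated performance is lost.

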The simulation results of the six scenarios were summarized in Figure 2-4 and Table 13-14. Figure 2 and Table 13 summarized the simulation results for the initial dose of Dose 3. Figure 3 and Table 14 summarized the simulation results for the initial dose of Dose 2. Figure 4 and Table 15 summarized the simulation results for the initial dose of Dose 1. For example, in Table 13, each scenario included two sub-tables. The upper sub-table contained 4 parts. The first part listed the target toxicity probability pT, the dose level, and true toxicity probabilities. The next three parts listed the selection probability, number of subjects treated, and the number of toxicities. The lower sub-table summarized four indicators that reflect the safety and reliability of the study, including the probability of selecting the true MTD, the probability of toxicity (proportion of subjects who have experienced DLT), the probability of select dose over-MTD, and the probability of no selection. Figure 2 showed these four indicators for all scenarios and all design methods in Table 13 by line graph.

[figure not shown]
Figure 2-4 and Table 13-14 showed that the i3+3 design has superior operating characteristics compared to the traditional 3+3 design. For example, in most scenarios, i3+3 has a higher probability of select true MTD, while having a smaller probability of select dose over-MTD.

* Mean ± Standard deviation. The statistics are calculated given by the current scenario and design setting.

Figure 2 Comparison of the i3+3 design with the 3+3 design (starting at Dose 3).

[figure not shown]

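### Section 4.2's MTD selection step lacks the upper limit and no-MTD outcome that Tables 13–15 appear to use, so the tabulated over-MTD rates are not those of the written rule

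*Protocol*

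**What the plan says.** Section 4.1 sends the reader to Section 4.2 for the MTD estimation method. Section 4.2 contains these elements:

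- **Selection.** After isotonic regression, "That is, if the toxicity probability of a dose is close to the target toxicity probability", the dose is taken as the MTD. For equal estimates below target the higher dose is taken; "if the estimate is greater than or equal to the target toxicity probability, the lower dose will be selected as the MTD".
- **No MTD.** The one case given is a DU recommendation at the lowest dose, when "the study should be terminated to ensure the safety and no dose level will be selected as the MTD". Otherwise the instruction is "Repeat the steps of 1) and 2) until the maximum sample size is reached".
- **Meaning of the equivalence interval (EI).** Before the decision table, the text explains that "the MTD should have a toxicity probability near 25% but not below 16% or above 30" percent. The selection step does not refer back to this.
- **Software.** "The MTD selection process can be implemented in the U-Design", with no settings given.

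The simulation setup in Appendix 8 lists its inputs ("Each cohort will enroll 3 subjects. The MTD target toxicity probability pT = 25" percent, the EI, and maximum sizes of 30, 36 and 42) but no selection limit. From Tables 13–15 it concludes that, in most scenarios, "i3+3 has a higher probability of select true MTD, while having a smaller probability of select dose over-MTD".

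**The concern.** The tables report sizeable probabilities of selecting no dose. The written rule can give that result only by stopping the trial at the lowest dose. If the tables came from a stricter selection rule than the one in Section 4.2, two things follow. Staff who apply the written step can name a higher dose than the simulated rule would. And the over-MTD rates used to justify i3+3 over 3+3 describe a different procedure. Finding the MTD is a primary objective, so the selection rule and its operating characteristics should belong together.

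**Working it through.** **1. Arithmetic on Table 13 (i3+3, 100 mg start, maximum 30; 1,000 runs in cohorts of 3).**

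*Scenario 6.* Subjects per dose: 0.765 + 12.828 + 14.844 + 1.422 + 0.132 + 0.009 + 0 = 30.000. No run stopped short. Selection probabilities: 0.025 + 0.849 + 0.106 + 0.006 = 0.986, so 0.014 select nothing, as the table states. That is 14 runs.

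*Scenario 1.* Subjects: 4.329 + 10.827 + 11.733 + 2.691 + 0.375 + 0.027 = 29.982. The shortfall is 0.018 × 1,000 = 18 subjects. A run that stops short loses at least 3, so at most 18 / 3 = 6 runs stopped short. The table has 49 runs with no selection.

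*Could DU at 25 mg in the very last cohort explain this?* Enrolment would then be full. If DU needs at least 3 DLTs, 14 such runs in scenario 6 need at least 14 × 3 = 42 DLTs at 25 mg; the table shows 0.038 × 1,000 = 38. Scenario 1 cannot be excluded by this count, but in the simulation below no MTD at full enrolment occurs in only 0.03% of its runs (0.01% in scenario 6).

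**2. Simulation of Appendix 7.** Inputs from the protocol: target 25%, EI 16–30%, cohorts of 3, maximum 30/36/42 for starts at 100/50/25 mg, and the Table 12 scenarios. Assumptions: close is read as closest; DU doses cannot be selected; isotonic regression is weighted by n; DU is called when P(DLT rate > 25%) > 0.95 under a uniform prior (2/3 gives 0.949, so it is not DU). There were 20,000 runs per cell.

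Probability of selecting a dose over the MTD, 100 mg start (%):

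| Scenario | Stated i3+3 | Section 4.2 step as written | With 30% limit | Tabulated 3+3 |
|---|---|---|---|---|
| 1 | 22.1 | 29.3 | 19.9 | 32.5 |
| 2 | 6.7 | 12.5 | 7.5 | 11.1 |
| 4 | 33.5 | 59.1 | 31.6 | 47.3 |
| 5 | 7.1 | 20.2 | 6.5 | 10.7 |
| 6 | 11.2 | 34.7 | 10.9 | 21.2 |

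No selection (stated / as written / with limit): scenario 1, 4.9 / 0.2 / 4.7%; scenario 6, 1.4 / 0.01 / 1.3%.

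Scenario 3 has no dose above the MTD, so 15 of the 18 cells apply. The written step exceeds the stated rate by 13.7 points on average. With the limit the mean gap is −0.4 and the largest 2.2.

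**3. Comparison with the tabulated 3+3.** The written step has the higher over-MTD rate in 14 of 15 cells. Seven are clearly beyond 1,000-run sampling error (scenarios 5 and 6 at all starts, scenario 4 at 100 mg). Three more are borderline, with z up to about 3. With the limit, none exceeds 3+3.

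True-MTD selection, written step / 3+3, 100 mg start, scenarios 1–6: 54.8/34.8, 64.9/44.6, 84.6/66.2, 40.9/52.7, 63.9/52.7, 64.6/68.5%. Over all starts the i3+3 advantage holds in scenarios 1, 2, 3 and 5 (12 of 18 cells) and fails in 4 and 6.

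**4. Sensitivity.**

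- *DU cut-off.* Mean enrolment in Table 15, scenario 4 is 22.062 + 2.409 + 0.372 + 0.045 = 24.888. The model gives 24.85 at 0.95, 15.7 at 0.90 and 27.9 at 0.98. At 0.98 the count above 3+3 is again 14 of 15 (mean gap +17.1). At 0.90 it is 3 of 15 (+3.0), but 0.90 does not fit the enrolment.
- *Limit value.* A 32% limit fits about as well on average, but gives 20.5% in scenario 4 at the 25 mg start (stated 15.6%; a 30% limit gives 14.7%).
- *Re-entry of DU doses.* Tabulated subject counts fit better if a DU dose can be used again: scenario 6, 100 mg start, 14.7 subjects at 100 mg with re-entry and 12.0 without (stated 14.844). The mean gaps become +15.3 (as written) and −0.1 (limit).

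**5. A single trial.** At 100 mg take 1/3, 2/6, 3/9, 4/12, 5/15, 6/18. From the second cohort on, each result is followed by a return to 50 mg, where 0/3, 0/6, 0/9 and 0/12 each send the trial back up. Every move follows Appendix 7, and the total is 18 + 12 = 30. The estimates are 0% (25 points from target) and 33% (8 points). The written step names 100 mg; the rule that reproduces the tables names 50 mg.

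**The case against.** The strongest reply is that Section 4.2 does contain an upper bound: its explanation of the EI says the MTD should not be above 30%, and a reader who applies the whole section would not name 100 mg in the example. That stands as far as it goes, so the fault is an unreconciled pair of statements rather than complete silence. But the same sentence also sets a floor of 16%. Applying both bounds gives about 76% no selection in Table 13, scenario 6, against 1.4% stated, and Appendix 8 counts a 10% dose as the true MTD there. No complete reading of that sentence reproduces the tables.

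It is also fair to say that close is not closest, that selection is meant to draw on all safety data, that Figure 1 is not shown, and that the sponsor may in practice run the same software with the same settings. These points make the simulated rates approximate and dependent on the DU assumption; with re-entry of DU doses, for example, scenario 6 as written rises to about 45%. They do not touch the enrolment sums. Finally, escalation itself is unaffected: the issue arises only at the end of the study.

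**Conclusion.** The point holds. Arithmetic on Table 13 shows no-selection rates that stopping at the lowest dose does not explain; scenario 6 needs only the premise that DU takes at least 3 DLTs. An upper limit of about 30% with a no-MTD outcome fits all three tables. The written step does not: its over-MTD rates are on average about 14 points above those stated, and in scenarios 4, 5 and 6 from the 100 mg start they clearly exceed the tabulated 3+3 rates. The sizes rest on the assumed 0.95 DU cut-off, which matches the published enrolment, and on reading close as closest.

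The claim of a smaller over-MTD probability is therefore unsupported for the rule as written. The claim of better true-MTD selection survives in four of the six scenarios. The comparison of the proportion of subjects with a DLT (lower for i3+3 in 14 of 18 cells) does not depend on selection and stands. The published tables remain usable for the rule that was actually simulated. This should be fixed, and it is cheap to fix.

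**What to change.** Check the U-Design settings behind Appendix 8 and write that rule into the selection step of Section 4.2, for example:

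> Candidates are doses that were tried, are not marked DU, and have an isotonic estimate not exceeding [upper limit used in Appendix 8; apparently the 30% EI bound, to be confirmed]. The candidate closest to 25% is the MTD, with ties resolved as stated. If there is no candidate, no MTD is declared. [If confirmed: the 16% EI bound is not a selection filter.]

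Reword the EI sentence so that it describes the interval and points to this rule. If no upper limit is intended, re-run Tables 13–15 under the written step and restate the comparison with 3+3 in Section 4.2 and Appendix 8.

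The cost is a few sentences after a settings check, or one re-run of the simulations. The limit has a price: compared with the written step, correct selection is about 4–10 points lower in scenarios 1–3, though 6–7 points higher in scenario 5, 17–28 in scenario 4 and 21–22 in scenario 6. The published tables already carry those lower figures, so adopting the simulated rule changes no reported result.
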